⁶⁸Ga PSMA-HBED-CC PET positive findings will be validated as true positive or false positive as outlined in more detail below. False negative ⁶⁸Ga PSMA-HBED-CC PET findings will only be determined when positive biopsies of ⁶⁸Ga PSMA-HBED-CC PET negative lesions that are present on conventional imaging are performed as part of standard clinical care. This scenario is uncommon.

⁶⁸Ga PSMA-HBED-CC PET validation based on follow-up imaging (CT, MRI, bone scan):

- 5.6.1. **Lymph nodes** ⁶⁸Ga PSMA-HBED-CC positive nodes will be assessed for change in size using standard of care follow-up imaging.
- 5.6.2. **PSMA-positive osseous or metastatic lesions.** ⁶⁸Ga PSMA-HBED-CC positive osseous or distant metastatic lesions will be followed by other imaging (bone scan, Naf PET, CT or MRI) at the treating physician's discretion and local standard of care.
- 5.6.3. **Biopsy.** Biopsies to determine metastases or provide information for re-staging should be performed at treating physician's discretion and per local standard of care.

5.7. **General Concomitant Medication and Supportive Care Guidelines**

In general, subjects may receive full concomitant and supportive care throughout this trial.

5.8. **Follow-Up**

5.8.1. **Active follow-up.** Subjects will be actively followed for acute adverse events for 10 radioactive half-lives rounded up to the calendar day (as per the established standard). With a half-life of 67.71 minute for ⁶⁸gallium, the active follow-up will be a minimum of 1 calendar day.

5.8.2. **Long term follow-up.** After the active follow-up period, the subject will return to standard follow-up with their physician. Subject's outcome will be followed through passive chart review. Contact with subject and/or subject's treating physicians may occur to better define treatment outcomes.

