12. EFFICACY ASSESSMENTS

Determination of efficacy requires two primary assessments.

The first assessment is the clinical read of the ^{68}Ga -PSMA-HBED-CC PET/CT scan. Trained readers will identify lesions positive for prostate cancer disease, and based on these results, will categorize specifically defined anatomical regions of the subject (Table 12.2) as positive for disease by ^{68}Ga -PSMA-HBED-CC PET/CT. Criteria are described in Section 12.1 below.

The second assessment is the reference standard determination of disease positivity or negativity also performed on the same specifically defined anatomical regions (Table 12.2). The reference standard definitions are described below, and consist of a combination of pathological confirmation, conventional imaging follow-up evidence, and serial PSA measurements. Criteria are described in Section 12.2 below.

For purposes of endpoints, four major regions are identified for final analysis as defined in Table 12.1. Each region is divided into subregions as defined in Table 12.2. All primary data from ^{68}Ga -PSMA-HBED-CC PET interpretations, pathology results, and conventional imaging results, will be collected per the subregions defined below. The final region assignments and results will be derived from the subregion data as applicable.

Region	Description
1	Prostate Bed
2	Pelvis outside of prostate bed including lymph nodes
3	Extrapelvic soft tissue, lymph nodes and organ metastases (non-bone)
4	Bone metastases

Table 12-1. Major Analysis Regions

Region 2: Pelvis outside of prostate bed	Region 3: Extrapelvic soft tissue	Region 4: Bone metastases
Right obturator	Lung	Spine
Left obturator	Liver	Ribs
Right external iliac	Pancreas	Pelvis
Left external iliac	Spleen	Extremities
Right internal iliac	Intestine	Skull
Left internal iliac	Mesentary	Sternum
Other pelvic regions	Brain	Clavicle
	Other soft tissue	Other bone
	Abdominal nodes	
	Thoracic nodes	
	Other nodes	

Table 12-2. Subregion Classification

12.1. **^{68}Ga -PSMA-HBED-CC PET Results Definition**

Imaging interpretation ^{68}Ga -PSMA-HBED-CC PET:

Local Interpretations: PET images will initially be interpreted by a board certified nuclear medicine physician or a board-certified radiologist experienced in reading PET at the time of the imaging study at the institution that the study is being performed. These interpretations will not be used for evaluation of the primary endpoint.

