in the 9-12 month window post-⁶⁸Ga-PSMA-HBED-CC scan. Follow up imaging will only be performed on subjects that have positive ⁶⁸Ga-PSMA-HBED-CC findings because conventional imaging assessment for disease is primarily targeting suspicious lesions identified by ⁶⁸Ga-PSMA-HBED-CC PET/CT. Interpretation of follow-up imaging will be performed by local read. Preferably, the follow-up conventional imaging should be the same modality/modalities as the initial staging work-up to allow for reproducible and accurate comparisons. Conventional imaging standards as described below will be used to determine tissue positive for prostate cancer disease. Conventional imaging will not be used to determine negative prostate cancer disease regions due to its inherently low negative predictive value.

Tissue positive for prostate cancer disease based on follow-up imaging:

12.2.2.1. Lymph nodes will be assessed by change in size.

i. Positive for disease:

- a. -For subjects undergoing systemic treatment (alone or in combination with targeted treatment): If on post-treatment follow-up imaging within 3-12 months, visually suspicious lymph nodes seen on CT or MRI decrease by more than 30% in short axis diameter and PSA declines by more than 50%.
 - If PSA increases by more than 25% (PCWG3 definition of recurrence) on systemic therapy, then an increase in the size of lesion by more than 20% in the short axis diameter will be considered a positive for disease.
- b. In subjects with localized suspected lymph node(s) receiving targeted treatment without concomitant systemic treatment there are two ways to achieve positive for disease designation:
 - If the subject shows a decrease of PSA by greater than 50% after targeted treatment and the lymph node does not enlarge (change in size less than 20% in the short axis diameter or less than 3 mm increase in short axis diameter) [OR]
 - If on post-treatment follow-up imaging within 3-12 months, lymph nodes seen on CT or MRI decrease by more than 30% in short axis diameter (with a minimum of 3 mm in change in size)
- c. For untreated subjects: If on follow-up imaging within 3-12 months, lymph nodes seen on CT or MRI increase by more than 20% in short axis diameter (with a minimum of 3 mm in change in size).

ii. Negative for disease:

- Conventional Imaging follow-up will not be used for assessment of negativity for disease.

iii. Indeterminate for disease

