- Regions with no lymph nodes determined to be positive by the conventional imaging criteria described above and without pathology will be designated regions indeterminate for prostate cancer disease.
- Subjects that have had neither pathology sampling, nor conventional imaging follow up will have all regions designated as indeterminate for disease by reference standard.

12.2.2.2. Visceral lesions (non-lymph node soft tissue or organ) and prostate bed and prostate lesions will be assessed by change in size.

i. Positive for disease:

- a. For subjects undergoing systemic treatment (alone or in combination with targeted treatment): If on post-treatment follow-up imaging within 3-12 months, visually conspicuous lesions seen on CT or MRI decrease by more than 30% in long axis diameter and PSA declines by more than 50%.
 - If PSA increases by more than 25% (PCWG3 definition of recurrence) on systemic therapy, then an increase in the size of lesion by more than 20% in the long axis diameter will be considered positive for disease.
- b. In subjects with localized suspected lesions(s) receiving targeted treatment without concomitant systemic treatment there are two ways to meet positive disease criteria:
 - If the subject demonstrates a decrease of PSA by greater than 50% after targeted treatment [*OR*]
 - If on post-treatment follow-up imaging within 3-12 months, lesions seen on CT or MRI decrease by more than 30% in long axis diameter (with a minimum of 3 mm in change in size)
- c. For untreated subjects: If on follow-up imaging within 3-12 months, lesions seen on CT or MRI increase by more than 20%

in long axis diameter (with a minimum of 3 mm in change in size).

ii. Negative for disease:

- Conventional Imaging follow up will not be used for assessment of negativity for disease

iii. Indeterminate for disease

- Regions with no visceral lesions determined to be positive by the conventional imaging criteria described above and without pathology will be designated as visceral regions indeterminate for prostate cancer disease.
- Prostate bed and prostate regions not determined to be positive by the conventional imaging criteria described above and without pathology will be designated as prostate regions indeterminate for prostate cancer disease.
- Subjects that have had neither pathology sampling, nor conventional imaging follow up will have all prostate and visceral regions designated as indeterminate for disease by reference standard.

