12.2.2.3. Bone lesions will be considered:

i. Positive for disease on baseline assessment:

- Any positive sclerotic lesion on the CT portion of the ⁶⁸Ga-PSMA-HBED-CC PET or on a separate CT obtained \leq 30 days before or after the PET/CT.
- Focal uptake on the baseline bone scan performed within one month of ⁶⁸Ga-PSMA-HBED-CC PET.
- Any MRI lesion in bone read as positive on the initial MRI performed within one month of ⁶⁸Ga-PSMA-HBED-CC PET.

ii. Positive for disease on follow up:

- Any new positive sclerotic lesion on CT within 12 months of ⁶⁸Ga-PSMA-HBED-CC PET scan
- Any new MRI bone lesion within 12 months of ⁶⁸Ga-PSMA-HBED-CC PET scan
- Any new focal uptake in bone within 12 months of ⁶⁸Ga-PSMA-HBED-CC PET scan

- In subjects with localized suspected bone lesion(s) receiving targeted treatment without concomitant systemic treatment:
- If the subject demonstrates a decrease of PSA by greater than 50% after targeted treatment.

iii. Negative for disease:

- Conventional Imaging follow up will not be used for assessment of negativity for disease

iv. Indeterminate for disease:

- Regions with no bone lesions determined to be positive by the conventional imaging criteria described above and without pathology will be designated bone regions indeterminate for prostate cancer disease.

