13.3. Definitions of ^{68}Ga PSMA-HBED-CC accuracy

13.3.1. True positive definitions

13.3.1.1. **^{68}Ga PSMA-HBED-CC PET/CT positive for nodal metastases by internal blind reader** – and pathology (if available) positive for that node, or node positive for disease by imaging as defined in Section 12.2.2.1 If this criteria is met, the subject is defined as true positive for nodal disease.

13.3.1.2. **^{68}Ga PSMA-HBED-CC PET/CT positive for visceral metastases by internal blind reader** – and pathology (if available) positive for that visceral lesion, or, visceral lesion positive for disease by imaging as defined in Section 12.2.2.2. If this criteria is met, the subject is defined as true positive for visceral disease.

13.3.1.3. **^{68}Ga PSMA-HBED-CC PET/CT positive for osseous**

metastases by internal blind reader - and pathology (if available) positive for that osseous lesion, or, osseous lesion positive for disease by imaging as defined in Section 12.2.2.3. If this criteria is met, the subject is defined as true positive for osseous disease.

13.3.1.4. A single nodal, visceral, or osseous region determined as true positive as defined above is sufficient to define the subject as true positive by ⁶⁸Ga PSMA-HBED-CC PET/CT.

13.3.2. **True negative definitions**

13.3.2.1. **⁶⁸Ga PSMA-HBED-CC PET/CT negative for nodal metastases by internal blind reader** – and pathology (if available) negative for disease, and, extra-pelvic node not positive for disease by imaging. If this criteria is met, the subject is defined as true negative for nodal disease.

13.3.2.2. **⁶⁸Ga PSMA-HBED-CC PET/CT negative for visceral metastases by internal blind reader** – and pathology (if available) negative for disease, and, visceral lesion not positive for disease by imaging. If this criteria is met, the subject is defined as true negative for visceral disease.

13.3.2.3. **⁶⁸Ga PSMA-HBED-CC PET/CT negative for osseous metastases by internal blind reader** - and pathology (if available) negative for disease, and, osseous lesion not positive for disease by imaging. If this criteria is met, the subject is defined as true negative for osseous disease.

13.3.3. **False positive definitions:**

13.3.3.1. **⁶⁸Ga PSMA-HBED-CC PET/CT positive for nodal metastases by internal blind reader**, pathology (if available) is negative, and imaging demonstrates that node is not positive for disease. If this criteria is met, the subject is defined as false positive for nodal disease.

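### A PET-positive nodal, visceral or osseous finding with no pathology and non-positive follow-up imaging is indeterminate under 12.2.2 but false positive under 13.3.3, so the secondary PPV has two possible denominators

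*Combined protocol and SAP*

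**What the plan says.** Two parts of the plan address the same finding.

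**Reference standard (12.2.2).** "Conventional imaging will not be used to determine negative prostate cancer disease regions due to its inherently low negative predictive value". For nodes, 12.2.2.1 iii follows through: "Regions with no lymph nodes determined to be positive by the conventional imaging criteria described above and without pathology will be designated regions indeterminate". Section 12.2.2.2 iii does the same for visceral lesions, and 12.2.2.3 iv for bone: "Regions with no bone lesions determined to be positive by the conventional imaging criteria described above and without pathology will be designated bone regions indeterminate".

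**Accuracy definitions (13.3.3).** Under 13.3.3.1 a PET-positive node is false positive when "pathology (if available) is negative, and imaging demonstrates that node is not positive for disease". Sections 13.3.3.3 (visceral) and 13.3.3.5 (osseous) are built the same way. None of the three refers back to 12.2.2, although the true positive items (13.3.1) and false negative items (13.3.4) do.

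Section 5.6 leans toward the second reading. It says that "PET positive findings will be validated as true positive or false positive as outlined in more detail below", and then introduces "PET validation based on follow-up imaging (CT, MRI, bone scan").

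Section 13.3.5.1 makes a region non-evaluable only when it meets none of the true or false positive or negative definitions.

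**The concern.** Per-subject and per-region PPV are the secondary efficacy endpoint (1.2.1, 13.2). Biopsy is sought only where clinically practicable (12.2.1), and follow-up imaging is the stated fallback. The study pays for a CT at 9 to 12 months if none has been done, with follow-up imaging confined to PET-positive subjects (12.2.2). A PET-positive finding with imaging but no tissue is therefore foreseeable.

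If such a finding is not positive on imaging, one part of the plan says that its status cannot be called negative, and another counts it against the tracer. Without a stated rule, the choice could be made after the data are seen. The plan also contemplates combining its results with those of sites using the same reference standard definitions (13.1, said there of sensitivity), which presupposes that the definitions give one answer.

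**Working it through.** **Step 1: apply both sections to one case.** Take a PET-positive node with no pathology and follow-up CT that does not meet the size or PSA criteria of 12.2.2.1 i.

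- 12.2.2.1 iii: the region is indeterminate.
- 13.3.3.1: with no pathology, only the imaging condition remains, and read literally it is met. The finding is false positive.
- 13.3.5.1: residual. It applies only if 13.3.3.1 is not met, so it cannot decide between the two.
- Precedence: the introduction to Section 12 points to 12.2 for reference status, and 13.2 points to 13.3 for accuracy. Neither overrides the other.

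Visceral and osseous findings give the same result.

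**Step 2: limits of the conflict.**

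- Per subject, one true positive region makes the subject true positive (13.3.1.4, 13.3.3.7). Only PET-positive subjects with no true positive region are affected. Per region there is no such override.
- With neither pathology nor follow-up imaging, nodal and visceral regions are indeterminate under 12.2.2, and the imaging condition in 13.3.3 is not met, so the sections agree. Bone is less clear, because 13.3.3.5 says only imaging, and 12.2.2.3 i counts the CT part of the PET/CT.
- The prostate bed is one of "four major regions are identified for final analysis as defined in Table 12.1", and 12.2.2.2 iii makes indeterminate "Prostate bed and prostate regions not determined to be positive by the conventional imaging criteria described above and without pathology". But 13.3.3 has no false positive rule for it unless it is read as visceral, so the conflict does not clearly reach it.

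**Step 3: size.** The plan states no PPV figure. Its only precision figures are the sensitivity half-widths in 13.1. These reproduce (at 80%: 1.96 × √(0.8 × 0.2/30) = 14.3%) but do not bear on this point.

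Let M be the PET-positive subjects who are true positive, pathology-negative or unresolved, N the pathology-negative ones, U the unresolved ones, and TP = M − N − U.

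- Unresolved excluded (12.2.2): PPV = TP/(TP + N)
- Unresolved as false positive (13.3.3): PPV = TP/M
- Difference = [TP/(TP + N)] × U/M

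The documents give none of these counts, so all are assumptions. Applying the detection rates in 2.3 (50% to 96.8%) to 30 patients gives 30 × 0.50 = 15 to 30 × 0.968 = 29 PET-positive subjects, an upper range for M. The midpoint is 22. N is set to 1 and counted as false positive under both rules. Intervals are Wilson 95%, as in 13.2.

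| U (M = 22, N = 1) | Excluded | As false positive | Difference, points |
|---|---|---|---|
| 0 | 21/22 = 95.5% | 21/22 = 95.5% | 0 |
| 1 | 20/21 = 95.2% (77.3–99.2) | 20/22 = 90.9% (72.2–97.5) | 4.3 |
| 2 | 19/20 = 95.0% (76.4–99.1) | 19/22 = 86.4% (66.7–95.3) | 8.6 |
| 4 | 17/18 = 94.4% (74.2–99.0) | 17/22 = 77.3% (56.6–89.9) | 17.2 |

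Varying the assumptions:

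- M = 15, N = 1, U = 4: 10/11 against 10/15, 24.2 points.
- M = 29, N = 1, U = 4: 24/25 against 24/29, 13.2 points.
- M = 22, N = 3, U = 4: 15/18 against 15/22, 15.2 points.
- Per region, with an assumed 33 PET-positive regions, 2 pathology-negative and 3 unresolved: 28/30 = 93.3% against 28/33 = 84.8%, 8.5 points. This is only indicative, because the four regions of Table 12-1 do not map one to one onto the nodal, visceral and osseous classes of 13.3.

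**The case against.** The strongest reply is that there is no ambiguity. Section 13.2 hands the definition of accuracy to 13.3, failing to be positive is a weaker condition than being negative, and 12.2.2 never says that an indeterminate region leaves the PPV denominator. Read literally, 13.3 gives one answer: false positive. The pathology qualifier runs through all the regional false positive items, so counting imaging-only cases may even be intended.

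Part of this stands. It is the more literal reading of 13.3, and 5.6 supports it. But the introduction to Section 12 sends the reader to 12.2 for disease positivity and negativity, and a false positive is a positive test in a region whose reference status is negative. On the literal reading, the plan counts as errors findings that it says imaging cannot show to be negative.

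The opposite rescue, that imaging can never show a lesion to be non-positive, fails as well. Imaging is a joint condition in all three rules, so they could then never be met, even with negative pathology.

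It is also fair that the number unresolved may be small. After targeted treatment alone, a PSA fall above 50% makes visceral and bone lesions positive, and makes nodes positive if they have not enlarged. Baseline CT, bone scan or MRI can make bone lesions positive (12.2.2.3 i).

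Three stronger inferences are not supported:

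- *That the primary endpoint is compromised.* The disputed findings are either false positive or non-evaluable. Neither enters TP/(TP + FN). They would enter only if the formula printed in 13.1, which has false positives in the denominator, were applied literally. That is a separate error.
- *That a negative bone biopsy has no route, so requiring negative pathology would all but abolish osseous false positives.* Section 12.2.1.3 sends negative bone biopsies to further evaluation and indeterminate ones to follow-up imaging. Its alternative diagnoses are given only as examples, and 13.3.3.6 remains a separate route. What is missing is whether a negative biopsy without an alternative diagnosis counts as indeterminate.
- *That a very large shift in PPV is to be expected.* No count in the documents supports any particular number unresolved.

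**Conclusion.** The conflict is real and should be resolved before analysis. For PET-positive nodal, visceral or osseous regions without pathology and with non-positive follow-up imaging, the plan supports two classifications and does not say which governs, so the secondary PPV is not uniquely defined.

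With 22 PET-positive subjects and 1 pathology-negative, both assumed, the shift is 0, 4, 9 or 17 points for 0, 1, 2 or 4 unresolved subjects. At 1 or 2 unresolved it is smaller than half the width of the Wilson interval with these subjects excluded (about 11 points), but it runs in one direction and is not sampling error. The figures also assume that every pathology-negative finding counts as false positive, although 13.3.3 adds an imaging condition.

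The consequence is bounded: PPV is secondary and descriptive in a 30-patient pilot, no decision rule uses it, and the primary endpoint is unaffected under the conventional sensitivity formula.

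**What to change.** Before the reads are analysed, align 5.6, 12.2.2, 13.3.3 and 13.3.5 on one rule. The rule that follows from the plan's own statement about low negative predictive value is:

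1. A PET-positive region without pathology and with non-positive imaging is non-evaluable for the main PPV.
2. Sections 13.3.3.1, 13.3.3.3 and 13.3.3.5 require negative pathology as defined in 12.2.1, and state whether the joint imaging condition still applies once pathology is negative.
3. A second, conservative PPV, per subject and per region, counts the unresolved findings as false positive. It is not a strict lower bound, because findings with neither pathology nor imaging stay out.
4. The numbers of non-evaluable regions and subjects are reported by reason.

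In the same edit, state whether a negative bone biopsy without an alternative diagnosis counts as indeterminate under 12.2.1.3, and so goes to follow-up imaging, and whether the prostate bed is classed as visceral throughout 13.3.

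The cost is wording and a little extra output, with no new data or procedures. The prostate bed clarification may also touch 13.3.1, 13.3.2 and 13.3.4. The downside is that the main PPV leaves out unresolved cases, which favours the tracer and leaves few routes to a false positive, so the conservative figure must be reported beside it.

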13.3.3.2. **⁶⁸Ga PSMA-HBED-CC PET/CT positive for nodal metastases by internal blind reader**, but pathology (if available) is positive for node but in a different nodal region than the node seen on PSMA PET. If this criteria is met, the subject is defined as false positive for nodal disease.

13.3.3.3. **⁶⁸Ga PSMA-HBED-CC PET/CT positive for visceral lesion by internal blind reader**, pathology (if available) is negative, and imaging demonstrates that the visceral lesion is not positive for disease. If this criteria is met, the subject is defined as false positive for visceral disease.

13.3.3.4. **⁶⁸Ga PSMA-HBED-CC PET/CT positive for visceral lesion by internal blind reader**, but pathology (if available) is positive for visceral lesion but in a different region than the visceral

region seen on PSMA PET. If this criteria is met, the subject is defined as false positive for visceral disease.

- 13.3.3.5. **^{68}Ga PSMA-HBED-CC PET/CT positive for osseous lesion by internal blind reader**, pathology (if available) is negative, and imaging demonstrates that the osseous lesion is not positive for disease. If this criteria is met, the subject is defined as false positive for osseous disease.
- 13.3.3.6. **^{68}Ga PSMA-HBED-CC PET/CT positive for osseous lesion by internal blind reader**, but pathology (if available) is positive for osseous lesion but in a different region than the osseous region seen on PSMA PET. If this criteria is met, the subject is defined as false positive for osseous disease.
- 13.3.3.7. A subject is defined as false positive for disease by ^{68}Ga PSMA-HBED-CC PET/CT if one or more regions as defined above are defined as false positive regions and the subject is not defined as true positive as defined in Section 13.3.1

13.3.4. **False negative definitions:**

- 13.3.4.1. **^{68}Ga PSMA-HBED-CC PET/CT negative for nodal metastases by internal blind reader**, and pathology (if available) positive for any node or positive for disease by imaging as defined in Section 12.2.2.1. If this criteria is met, the subject is defined as false negative for nodal disease.
- 13.3.4.2. **^{68}Ga PSMA-HBED-CC PET/CT negative for visceral lesion by internal blind reader**, and pathology (if available) positive for any visceral lesion, or, visceral lesion positive for disease by imaging as defined in Section 12.2.2.2. If this criteria is met, the subject is defined as false negative for visceral disease

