- 13.3.4.3. **^{68}Ga PSMA-HBED-CC PET/CT negative for osseous lesion by internal blind reader**, and pathology (if available) positive for any osseous lesion, or, osseous lesion positive for disease by imaging as defined in Section 12.2.2.3. If this criteria is met, the subject is defined as false negative for osseous disease.
- 13.3.4.4. A subject is defined as false negative for disease by ^{68}Ga PSMA-HBED-CC PET/CT if the subject is negative for disease in all regions by ^{68}Ga PSMA-HBED-CC PET/CT, but positive for disease by pathology or follow-up imaging in any region.

13.3.5. **Non-evaluable definitions:**

- 13.3.5.1. Any region that does not have sufficient data to meet the criteria for definition of true positive region, true negative region, false positive region, or false negative region will be classified as non-evaluable.
- 13.3.5.2. Any region that does not have sufficient data to meet the

criteria for definition of true positive subject, true negative subject, false positive subject, or false negative subject will be classified as non-evaluable.

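### Even with the sensitivity formula corrected, the subject-level rules drop men with biopsy-proven disease that PET missed if their only PET uptake is elsewhere and unconfirmed

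*Combined protocol and SAP*

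**What the plan says.** Section 13.2 makes per-subject sensitivity the primary endpoint, with a Wilson 95% interval. Section 13.3 supplies the subject classes.

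- **True positive.** 13.3.1.4: "A single nodal, visceral, or osseous region determined as true positive as defined above is sufficient to define the subject as true positive". For nodes, 13.3.1.1 requires a PET-positive read and "pathology (if available) positive for that node, or node positive for disease by imaging as defined in Section 12.2.2.1".
- **False positive.** 13.3.3.2 covers a PET-positive nodal read where "pathology (if available) is positive for node but in a different nodal region than the node seen on PSMA PET". 13.3.3.4 and 13.3.3.6 do the same for visceral and osseous disease. 13.3.3.7 then makes the subject false positive if any region is false positive and he is not true positive.
- **False negative by disease type.** 13.3.4.1 requires PET to be negative for nodal metastases "and pathology (if available) positive for any node or positive for disease by imaging as defined in Section 12.2.2.1". 13.3.4.3 is the osseous counterpart, ending "the subject is defined as false negative for osseous disease".
- **False negative subject.** 13.3.4.4: a subject is false negative "if the subject is negative for disease in all regions by" PET/CT, "but positive for disease by pathology or follow-up imaging in any region".
- **Non-evaluable.** 13.3.5.2: whatever is too thinly documented to satisfy "criteria for definition of true positive subject, true negative subject, false positive subject, or false negative subject will be classified as non-evaluable". Its opening words refer to a region, but the classes it lists are subject classes.

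**The concern.** A sensitivity denominator should hold everyone the reference standard calls diseased. Here a subject enters it in only two ways: a PET-positive finding is confirmed, or PET is clean everywhere and disease is found. A man in whom PET missed the proven site and marked only some other, unconfirmed site fits neither. He is a failure of localisation, and the endpoint is about detecting tumour location, yet he does not count against sensitivity.

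Section 5.6 describes confirmed false negatives as uncommon, so the misses that do get counted may be few. Section 13.1 says the pilot's result will help choose the sensitivity used to power a larger study, so an upward error would be carried forward.

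**Working it through.** **1. The plan's own figure.** Section 13.1 tabulates half-widths for 30 patients by normal approximation. At 80%: 1.96 × √(0.80 × 0.20 / 30) = 14.3 points, as printed. The other four rows also reproduce (16.4, 15.5, 12.8, 10.7).

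**2. The formula.** As printed, the denominator is TP+FP. Men classed FP are inside it and leave once it is corrected to TP+FN. Non-evaluable men are outside it either way. So correcting 13.1 alone does not bring in all reference-positive men.

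**3. Two cases put through the rules.** In both, PET marks a pelvic node that is not biopsied and shows no qualifying size change.

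| | Case 1 | Case 2 |
|---|---|---|
| PET-missed, biopsy-proven site | Retroperitoneal node, itself not meeting the size criteria of 12.2.2.1 | Bone lesion |
| TP subject (13.3.1.4)? | No: no PET-positive finding is confirmed | No: PET is negative for bone and the pelvic node is unconfirmed |
| FN by disease type? | No: PET was positive for a node, so 13.3.4.1 fails | Yes, osseous (13.3.4.3) |
| FN subject (13.3.4.4)? | No: PET not negative in all regions | No: same reason |
| Where he ends | FP (13.3.3.2 with 13.3.3.7), or non-evaluable because the marked region is indeterminate (12.2.1.5, 12.2.2.1 iii, then 13.3.5) | Non-evaluable by the same route, or FP if 13.3.3.1 is read to apply without pathology |

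If the missed sites were seen on conventional imaging and biopsied in routine care, Section 5.6 would count both as false-negative findings. The text does not settle FP against non-evaluable, but either takes the man out of TP+FN.

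**4. Is this the only leak?** Take two regions, each PET positive or negative and each reference positive, negative or indeterminate, with at least one reference-positive. That gives 4 × 5 = 20 patterns: 11 are TP, 5 FN, 2 FP and 2 neither. The last four are one situation and its mirror image: proven disease where PET is negative, with PET uptake in the other region that is reference-negative (FP) or indeterminate (non-evaluable). Every excluded man is a PET miss.

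**5. Size.** Let N be the number of reference-positive men and d the number dropped. The estimate becomes TP/(N − d) instead of TP/N, so it is multiplied by N/(N − d). The documents give neither d nor the reference-positive count; the values below are assumptions.

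| TP | N | d | Estimate | Wilson 95% CI |
|---|---|---|---|---|
| 24 | 30 | 0 | 80.0% | 62.7–90.5% |
| 24 | 30 | 1 | 24/29 = 82.8% | 65.5–92.4% |
| 24 | 30 | 2 | 24/28 = 85.7% | 68.5–94.3% |
| 18 | 24 | 0 | 75.0% | 55.1–88.0% |
| 18 | 24 | 2 | 18/22 = 81.8% | 61.5–92.7% |

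The multiplier for d = 1 and d = 2 is 1.034 and 1.071 at N = 30, and 1.071 and 1.154 at N = 15. With d = 0 there is no error.

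**6. Matching level.** In 13.3.1 the pathology limb is tied to the lesion PET marked; the imaging limb is not. 13.3.3.6 separates osseous regions, but Table 12-1 has one bone region, and Section 12 names four major regions for final analysis. The choice matters. If two of the six missed men in the 24/30 example had uptake in a rib and proven disease in the spine, matching on the single bone region would credit them as TP: 26/30 = 86.7%.

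**The case against.** The best defence is that this is partly a deliberate convention. Sections 13.3.3.2, 13.3.3.4 and 13.3.3.6 expressly call wrong-region disease false positive. Treating unresolved uptake as non-evaluable is also defensible, because 12.2.2 does not let conventional imaging prove a region negative and the uptake may be real disease. The situation needs a proven miss, uptake elsewhere and no confirmed PET finding, all in one man. The study is a 30-patient pilot without significance testing, and the illustrated shifts are smaller than its sampling error.

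Much of that stands. The frequency is unknown, the consequence is modest, and the upward direction holds only against the plan's reference standard, not against true disease status. But false positive is a class for predictive value; assigning it does not explain why a man with proven disease should leave the sensitivity denominator. 13.3.4.4 says if rather than only if, yet no other rule makes a subject false negative.

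Three stronger readings are tempting and not supported:

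- *Most PET misses fall in this gap, because only PET-positive men get follow-up imaging.* The documents conflict on who is imaged: one sentence in 12.2.2 restricts it to PET-positive subjects, while the opening of 12.2.2 and 6.4.3 do not. 12.2.2.3 i also accepts the CT part of the study scan for bone. No share can be inferred.
- *13.3.1 already requires lesion-level matching throughout.* Only its pathology limb does. Read literally, a PET-positive man with a different imaging-positive lesion of the same type could be TP.
- *Misses shown by imaging alone are dropped too.* That depends on whether 13.3.4 prevails over 5.6, which recognises false negatives only through biopsy, and on how the imaging limb of 13.3.1 is read.

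**Conclusion.** The gap is real for biopsy-proven misses. With the denominator corrected to TP+FN, a man with proven disease at a PET-negative site and only unconfirmed uptake elsewhere is in neither term, even where 13.3.4.3 calls him false negative for osseous disease. Each such man removed raises the estimate by about 3 points at the plan's 80% row, if all 30 men are reference-positive. That is within sampling error, but a one-directional error is not covered by the interval. Because d is not in the documents, these figures are illustrations, not a forecast. This should be fixed before reads are classified; it does not invalidate the pilot.

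**What to change.** Define the per-subject sensitivity denominator as every subject who is reference-positive in at least one region. Replace 13.3.4.4 with: false negative means reference-positive in any region and not true positive under 13.3.1. Use false positives for predictive value only, and state that one subject may be false negative for sensitivity and false positive for predictive value.

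Report how many false-negative subjects had PET uptake only at indeterminate sites, and give sensitivity without them as a supporting analysis.

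State the level at which PET and reference findings are matched for a true positive. Lesion or sub-region matching would tighten the imaging limb of 13.3.1 and must be reconciled with the four major regions of Section 12 and with the statements in 12.1.1.1 to 12.1.1.3 that sub-region data are not used directly for the endpoints. Major-region matching can credit PET with sites it missed.

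The cost of the denominator change is wording. Findings are already collected by sub-region, and no patients or procedures are added. Two downsides: a subject no longer has a single class, and counting men with indeterminate uptake as false negative is conservative.

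The conflict between 5.6 and 13.3.4, the conflict over who receives follow-up imaging, and the status of the prostate bed are separate points to reconcile.
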